AURORA HEALTH CARE, INC.

PROTOCOL TITLE: Pilot study for the efficacy and tolerability of Senokot-S[®] in the treatment of diabetic gastroparesis

PRINCIPAL INVESTIGATOR:

[name] Hospitalist [name] [contact] [contact] Email: [contact]

INVESTIGATORS AND KEY PERSONNEL:[name], [name], [name]

This protocol was designed and developed by Aurora Healthcare, Inc. It is intended to be used only in conjunction with institution-specific IRB approval for study entry.

I. Background and Significance

Diabetic gastroparesis can be a difficult-to-treat complication of longstanding diabetes that can significantly compromise quality of life in those affected. Today there is only one medication approved by the FDA for the indication of diabetic gastroparesis and it has received a black box warning due to potential for severe neurological side effects. There are other medications that have found some success in the treatment of diabetic gastroparesis, but they also have the potential for serious side effects, and some are only available through a special use program.¹

II. Specific Aim

The aim of the study is to evaluate the efficacy of the stimulant laxative Senokot-S[®] for the treatment of diabetic gastroparesis. Senokot-S, and its metabolites, are thought to produce peristalsis, drive intra-luminal fluid and electrolyte shifts, and have an irritant effect on the gut mucosa^{2,3}. These complex physiologic mechanisms appear may sufficiently promote stomach emptying, and thereby reduce or eliminate the severity of gastroparesis symptoms. In this open label study, participants will be randomized into high and low dose groups to assess for ideal dosing and tolerability. It is the overall goal of this study to select the most promising dose-strength for the treatment of mild through severe gastroparesis.

(c) Study End Points

- a. Primary Endpoint
 - i. Modified GCSI-DD: Subjects will complete the modified Gastroparesis Cardinal Symptom Index-Daily Diary (mGCSI-DD)^{4,5}. The mGCSI-DD is a validated patient reported outcome (PRO) instrument with excellent testretest reliability, and will be used as the primary instrument to assess for efficacy in this study.

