 - ii. Questions on the mGCSI-DD are a 6-point Likert scale from 0 (none) to very severe (5) that address: nausea, retching, vomiting, stomach fullness, ability to finish a normal-sized meal, feeling excessively full after meals, loss of appetite, bloating, external assessment of stomach size, upper ab-dominal pain or discomfort.
- b. Secondary Endpoint
 - i. Breakthrough medication use: Defined as the change in the frequency of use of breakthrough medication, which is the medication that has been previously prescribed on an as-needed basis to manage symptoms.

Any change in frequency of use of breakthrough medications will be used as a secondary endpoint to assess for efficacy in the study.

 Bowel habits: Subjects will self report bowel habits during the baseline week and through the study period on the same questionnaire form. Since Senokot-S functions primarily as a mild bowel stimulant any significant change in bowel habits will help to assess for tolerability in this study.

IV. Study Design

The Phase II study design will be an open label, pre- and post-treatment assessment, prospective study. Sixty (60) study participants will be recruited over a 5-month period at a single site. Participants will be randomized into two treatment groups, a high- and low-dose, and will take medication dosed orally, twice daily or once daily at night.

V. Experimental Design, Methods, and Study Procedures

- **a.** Initial Identification of Potential Study Subjects Gastroenterologists who have agreed to refer their patient with diabetic gastroparesis for this study will make the initial contact with those patient (study inclusion/exclusion criteria will be provided to these physicians for ready reference). If the patient is interested in participating in the study the gastroenterologists will secure the patient's verbal permission to provide their name and contact information (phone or e-mail) to [name] or another member of the study team. The study team member will contact the patient and arrange a time to meet with them to explain the study and to answer any questions the potential subject may have.

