- b. Screening Visit The screening visit will include reviewing the participants' complete medical history after reviewing and obtaining informed consent. Data from the participant's medical history will be abstracted from the electronic medical record (EMR) and will be securely stored with other study-related data. Participants will be given the mGCSI-DD questionnaire and instructed on its use. At this visit participants will start recording their week of baseline scores by filling out a separate mGCSI-DD questionnaire and Breakthrough Medication Use and Bowel Habits documentation form daily.
- c. Visit 1 will occur 1 week after the screening visit. Participants will return with their mGCSI-DD baseline week of scores. They will be sequentially randomized (1:1) into either the high (8.6/50mg of senna/docusate taken by mouth twice daily) or low (8.6/50mg of senna/docusate taken by mouth once every night) dose study group. To reduce potential subject bias and placebo effect, participants will not be informed as to which dose of study medication they are randomized. They will be given their study medication and their 28-day mGCSI-DD questionnaire sheets, along with a pre-printed return envelope for use after completing their month of treatment in the study. They will be instructed to decrease use of any previously prescribed breakthrough medication as can safely be tolerated. Examples of these medication may include prokinetics such as Reglan (metoclopramide), erythromycin, or domperidone; anti-emtics such as Zofran (ondansetron), or Compazine (prochloperazine); or analgesics such as tramadol,

hydrocodone, or oxycodone. They will also be instructed to resume any breakthrough medication use as previously prescribed at the completion of the study and to continue routine follow ups with their care providers.

Subjects will be instructed to immediately contact the Principal Investigator if they experience episodes of significant diarrhea or rectal bleeding.

Participants may be notified by phone at the end of their study period to verify data or request missing data.

VI. Risks

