Senokot-S side effects. Known side effects of Senokot-S include diarrhea, nausea or vomiting, stomach pain, rectal bleeding, gas, abdominal bloating, and potential for allergic reaction such as skin rash. There have been safety concerns in the past about potential complications from long term use of stimulant laxatives like Senokot-S, such as cathartic colon, increased incidence of colorectal cancer, and liver disease. Several recent studies and reviews refute those previous conclusions and suggest long-term use of mild stimulant laxatives is likely safe when needed^{3,6,7}. Senokot-S is listed as pregnancy category C by the FDA. Women with child bearing potential will be required to use an effective form of birth control while participating in this study.

Ineffective treatment of diabetic gastroparesis. Since this medication has not yet been studied in the treatment of diabetic gastroparesis it is possible that symptoms of the disorder may worsen. The common symptoms of diabetic gastroparesis include nausea, vomiting, postprandial fullness, early satiety, and abdominal pain.

Loss of confidentiality. It is expected that this risk will be low because of numerous safeguards that will be in place, including standard data management procedures with Aurora Health Care.

VII. Benefits

A successful outcome in the proposed study will have immediate implications by reducing the symptoms of diabetic gastroparesis. Such a result will address the significant unmet need by providing a safe, inexpensive pharmacological therapy for a difficult to treat chronic disorder. These findings would allow patients to reduce or eliminate intake of the only FDA-approved therapeutic medication, Reglan[®], which has a black box warning and unfavorable side-effect profile. These known potential benefits are highly likely to outweigh the potential risks of the intervention in this study.

VIII. Study Population

Inclusion Criteria:

- Age 18-75 years, male and non-pregnant, non-lactating females
- Diagnosis of type 1 or type 2 diabetes mellitus
- Clinical diagnosis of diabetic gastroparesis

Exclusion Criteria:

- Diagnosed idiopathic gastroparesis
- A history or inflammatory bowel disease, such as Crohn's disease or ulcerative colitis
- A history of bowel obstruction, current unexplained abdominal pain, or undiagnosed rectal bleeding
- Gastrointestinal cancer
- Any active cancer
- Prior gastric surgery
- End-stage heart disease, liver disease, lung disease

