Access to data housed in REDCap Cloud and associated with this research study will be limited to those individuals listed on the IRB approved research study, as well as caregivers from Research Analytics for administrative reasons. Study team members access to the system and the data itself will be limited in accordance with need (i.e., biostatisticians may be limited to simply export the dataset to statistical tools, research coordinators may be limited to entering data, etc.). Overall, limiting access to study team members by need should reduce the risk of accidental disclosure and breach of confidentiality. However, using a cloud-based application may incidentally raise the risk of a breach in confidentiality, and, therefore, Aurora Health Care, Inc. has negotiated strong protections with the vendor in the event of a breach of confidentiality.

XII. Statistical Plan

All category and continuous variables will be described using appropriate descriptive statistics such as frequency, percentage for category variables and mean, standard deviation, median, and range for continuous variables. Pre and post outcomes variables for two groups of patients in the experimental groups will be compared using appropriate parametric and/or non parametric statistical tests. For all statistical tests an alpha level of 0.05 will be used and all statistical analysis will be carried out using SAS version 9.4, SAS Institute, Cary, NC.

XIII. Monitoring Plan

Data monitoring, safety monitoring, and statistical analysis will be done through the research office and principal investigator.

Participants can stop the study at any time for any reason and can resume previous treatments whenever needed. Stopping points will be at the end of the 5 month study period or if a negative trend in mGCSI-DD post-treatment scores is observed.

XIV. Regulatory Requirements

The investigators and all key personnel agree to abide by the determinations of the Aurora IRB, including obtaining documented informed consent prior to inclusion of any individual in this research study. The investigators and all key personnel will comply with reporting requirements as outlined in the Aurora IRB Standard Operating Procedures (SOPs). In addition, investigators will permit access for on-site monitoring by representatives of the Aurora IRB, the Aurora Research Institute Investigator-Initiated Research unit, and the Aurora Research Institute Quality Improvement Program.

XV. References

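### Participants go from returning the baseline diary straight to 1:1 allocation, with no check that the week is usable, no stratification on baseline severity and no planned baseline adjustment

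*Combined protocol and SAP*

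**What the plan says.** The steps run in this order:

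- **Eligibility (Sections VIII and IX).** The disease criterion is "Clinical diagnosis of diabetic gastroparesis". No entry criterion uses the mGCSI-DD or a count of diary days. Section IX completes final screening at the in-person screening visit.
- **Baseline week (Section V.b).** "At this visit participants will start recording their week of baseline scores", one form per day. The scores therefore exist only after eligibility has been settled.
- **Allocation (Section V.c, Visit 1).** "Participants will return with their mGCSI-DD baseline week of scores. They will be sequentially randomized (1:1". Nothing stands between the returned diary and the assignment. No stratification factor, block size or minimisation is given.
- **Missing data (end of Section V.c).** The one step described is an optional phone call once the participant's study period is over.
- **Analysis (Section XII).** Pre and post outcomes "will be compared using appropriate parametric and/or non parametric statistical tests". No covariate is named.
- **Goal (Section II).** The study is to "select the most promising dose-strength for the treatment of mild through severe gastroparesis". No severity class is defined.

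**The concern.** The primary endpoint is a change from the baseline week, so each participant needs a usable week. If a diary comes back mostly blank, Visit 1 is the last point at which another untreated week can be collected. The phone call comes after the 28 days of treatment, so the participant would be recalling symptoms from four to five weeks earlier.

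The second issue is the dose contrast. Each item runs from 0 to 5, so a participant cannot improve by more than the baseline score, and those who start higher have more room to fall. If one arm starts more severe by chance, an unadjusted comparison of change scores carries part of that gap into the apparent dose effect. The study exists to choose between two doses across a range of severity, so this comparison matters.

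**Working it through.** **Inputs from the protocol.** "Sixty (60) study participants will be recruited over a 5-month period at a single site" (Section IV) at 1:1 gives about 30 per arm. "For all statistical tests an alpha level of 0.05 will be used" (Section XII) does not state sidedness; two-sided is assumed. The protocol gives no power, effect size, SD, dropout rate or baseline distribution, so it has no figure to reproduce. The shares used in steps 3 to 5 are assumptions, shown as ranges.

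**1. Chance gap in mean baseline score.** With 30 per arm, the standard error of the difference in means, in baseline SD units, is √(1/30 + 1/30) = 0.258. The probability of a gap of at least t SD is 2 × [1 − Φ(t/0.258)].

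- t = 0.25: 2 × [1 − Φ(0.968)] = 0.333
- t = 0.5: 2 × [1 − Φ(1.936)] = 0.053

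**2. How a gap enters the result.** Let β be the slope of the post-treatment score on the baseline score. For a baseline gap g, the unadjusted contrast in change scores shifts by (1 − β) × g. For β between 0 and 1 and g = 0.25 SD, the shift lies between 0 and 0.25 baseline SD. ANCOVA estimates β and removes the shift.

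**3. Chance gap in the share of severe participants.** This is the probability of a difference of at least 20 percentage points between arms, without stratification. The method of sequential randomisation is not described, so two schemes are shown.

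| Severe share of the 60 (assumed) | Fixed 30/30 split (hypergeometric) | Independent coin toss (simulation) |
|---|---|---|
| 20% | 10% | 6% |
| 33% | 17% | 12% |
| 50% | 20% | 16% |

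**4. Unusable baseline weeks.** With 30 per arm, the difference detectable with 80% power is (1.96 + 0.84) × 0.258 = 0.72 SD. The table shows the effect on that difference if participants without a usable week leave the comparison.

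| Unusable (assumed) | Evaluable per arm | Power for 0.72 SD | Randomised to keep 60 evaluable |
|---|---|---|---|
| 0% | 30 | 80% | 60 |
| 10% | 27 | 76% | 60/0.9 → 67 |
| 20% | 24 | 71% | 60/0.8 = 75 |
| 30% | 21 | 65% | 60/0.7 → 86 |

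**5. How many days make a usable week.** The reliability of a mean of k days is k × ICC / [1 + (k − 1) × ICC], where ICC is the day-to-day intraclass correlation (assumed).

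| ICC | 1 day | 5 days | 7 days |
|---|---|---|---|
| 0.4 | 0.40 | 2.0/2.6 = 0.77 | 0.82 |
| 0.6 | 0.60 | 3.0/3.4 = 0.88 | 0.91 |
| 0.8 | 0.80 | 4.0/4.2 = 0.95 | 0.97 |

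Five days lose little against seven. A single day loses much more unless days are very alike.

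**The case against.** **The case against.** Randomisation already balances severity in expectation, valid tests allow for chance imbalance, and a gap of 0.5 SD is unlikely (about 5%). Section V.b asks for daily completion, Section V.c speaks of a week of scores, and Section XI describes query management. Nothing says that one completed day is enough. This is a pilot, and entry on a clinical diagnosis suits a goal that includes mild disease.

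Most of this stands. It would be wrong to say that severity is unbalanced by design; the gap is that allocation is unstratified and no adjustment is planned. That a mostly blank week would be randomised follows from the absence of a rule, not from any statement. What remains is that no usable-diary rule exists and that the only described retrieval of missing data comes after treatment.

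**A stronger reading that does not hold.** A reader might infer that participants with near-zero scores should be kept out by a minimum baseline score, since on the primary instrument they can only stay level or worsen. The documents do not support this, for four reasons.

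- Selecting on the same week that serves as the pre-treatment value builds regression to the mean into a pre/post change that has no placebo arm, in the direction of apparent benefit.
- No threshold has a basis in the protocol, and a floor may remove mild participants whom Section II means to cover.
- A participant controlled on as-needed medication can still show benefit on the breakthrough-medication endpoint in Section II.
- The gain is small. Suppose a fraction f does not change at all and the others have a standardised change d. Dilution then multiplies the sample size needed for the pre/post change by (1 + f·d²)/(1 − f). With d = 0.5 (assumed) and f = 10%, 20% or 30%, this is 1.14, 1.31 or 1.54. Screening those people out already needs 1/(1 − f) = 1.11, 1.25 or 1.43 times as many starting the baseline week. The net gain per person screened is only 1 + f·d², or 2.5% to 7.5%, and recruitment is limited to five months at one site.

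**Conclusion.** The concern holds as a gap in design and analysis that is inexpensive to close. Final screening ends before any baseline score exists, allocation follows the returned diary without a usability check, and severity enters neither the allocation nor the planned comparison.

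The firmest figures are the chance gaps in mean baseline score: about 33% for at least 0.25 SD and about 5% for at least 0.5 SD. They rest only on 30 per arm and a normal approximation. The 6% to 20% chance of a 20-point gap in severe share depends on the assumed share and allocation scheme. The power losses depend on the assumed rate of unusable diaries. That rate may prove low, since participants are specialist referrals instructed to complete the diary daily.

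The point does not show that the trial will be biased, that the baseline diary goes unused, or that low scorers should be excluded.

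**What to change.** 1. **Usable-diary rule.** In Section V.c, check the returned diary before assignment. Require a pre-set minimum number of completed days (for example 5 of 7) and allow one repeat of the baseline week if it is not met. State which week then counts as baseline and what happens if the repeat also falls short. Amend Section IX so that final eligibility closes at Visit 1.
2. **Stratified allocation.** Stratify the 1:1 allocation by baseline-week mean mGCSI-DD below or above one cut, which the sponsor sets in advance.
3. **Baseline adjustment.** In Section XII, name ANCOVA with the baseline score as a covariate for the dose comparison.
4. **Severity reporting.** Report dose results by severity descriptively only. With equal strata there are about 15 participants per cell, and 80% power is reached only near (1.96 + 0.84) × √(2/15) = 1.0 SD. Limit the conclusion to the severity range actually enrolled.

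Do not add a minimum-score entry rule.

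**Cost.** Some participants are delayed by a week, a few may not qualify after the repeat, and a two-stratum allocation list is needed. The scores are already in hand at Visit 1, so the only extra data collection is the repeat week for those who need it.

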- Known or suspected drug abuse
- Any condition requiring use of daily narcotics
- Concurrent usage of mineral oil or products containing mineral oil
- Current or recent (within the last 3 months) usage of Senokot-S, docusate or senna

IX. Recruitment and Screening

Recruitment will occur through care provider referrals. Clinicians will be notified of the study through paper advertisement and posters. Initial screening will be done over the phone or through e-mail at the time of referral and will include a medical record review. Final screening and informed consent will be completed during the formal in person screening visit between the participant and research staff and is expected to take about one to two hours.

X. Privacy Plan

Patients will initially be notified of the potential to be in a research study by a current caregiver. If the patient is agreeable to consideration for the study the research team will be contacted by phone or through e-mail by the clinician with the patient's contact information. The patient will then be contacted by a member of the research team via an institution-based phone or EMR e-mail (based on the patient's preference) for initial screening and to set up a clinic visit for final screening and informed consent.

XI. Data Collection

The data to be collected will include a complete medical history of the participant, mGCSI-DD score forms, medication usage and bowel habits forms. Data will not be shared with any outside institutions.

This research study plans to store and manage the subject lists, demographic information, validated questionnaire, study and breakthrough medication use, and bowel habits datasets in REDCap Cloud, a secure electronic data capture application that is based on Vanderbilt University's REDCap application. Flexible for a variety of types of research, REDCap Cloud provides an intuitive data-entry interface for end users into study-specific data collection forms associated with study events. The application includes real time validation rules and query management, audit trails, and the automated export of study data into statistical programs. The REDCap Cloud platform is compliant with GCP predicate rule requirements and US FDA 21 CFR Part 11 pertaining to the use of electronic records and signatures. Aurora Health Care, Inc. has executed an agreement for use of the application with nearly all research studies conducted at Aurora.

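### A pre/post fall in breakthrough medication cannot be credited to the drug, because all participants are told to cut it when the drug starts

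*Combined protocol and SAP*

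**What the plan says.** Four parts of the combined protocol and SAP bear on this point.

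- **The endpoint.** Under Study End Points (Secondary Endpoint), breakthrough medication is defined as "the medication that has been previously prescribed on an as-needed basis to manage symptoms". The section continues: "Any change in frequency of use of breakthrough medications will be used as a secondary endpoint to assess for efficacy".
- **The baseline.** Under V.b (Screening Visit), participants spend a week "filling out a separate mGCSI-DD questionnaire and Breakthrough Medication Use and Bowel Habits documentation form daily". No instruction to reduce breakthrough medication is described for that week.
- **The instruction.** Under V.c (Visit 1), one week later, participants are randomised 1:1 to one of two doses of the same product. "They will be given their study medication and their 28-day mGCSI-DD questionnaire sheets". At the same visit: "They will be instructed to decrease use of any previously prescribed breakthrough medication as can safely be tolerated". The examples given are prokinetics, anti-emetics and analgesics. The direction is not restricted to one arm.
- **Design and analysis.** Section IV describes an "open label, pre- and post-treatment assessment, prospective study" with 60 participants in a high- and a low-dose group. Section XII says: "Pre and post outcomes variables for two groups of patients in the experimental groups will be compared using appropriate" parametric or non-parametric tests, at an alpha of 0.05. It does not say whether the test is within group or between doses.

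**The concern.** The protocol tells participants to make a change and then counts that change towards efficacy. The instruction and the drug begin at the same visit, directly after the only period that can serve as baseline. No untreated or placebo arm receives the same instruction, there is no run-in under it, and no analysis rule separates the two causes.

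Any uncontrolled pre/post comparison is open to expectation and regression to the mean. The instruction adds a cause that acts directly on this endpoint. If breakthrough use is tested pre versus post, which section XII permits, an inert product could show a significant reduction and be reported as supporting efficacy. That would matter to readers, because section VII presents lower reliance on metoclopramide as a benefit of a successful result, and metoclopramide is one of the breakthrough drugs named in V.c.

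**Working it through.** The plan gives no effect size, SD, baseline frequency or power calculation for this endpoint, so there is no figure to reproduce. The attribution problem follows from the order of events; the arithmetic only shows how it could play out.

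**Order of events**

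| Period | Drug | Told to reduce breakthrough use |
|---|---|---|
| Baseline week | No | Not described |
| 28 treatment days, high dose | Yes | Yes |
| 28 treatment days, low dose | Yes | Yes |

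Drug and instruction change together between the first row and the other two, so the pre/post contrast estimates their sum, together with any expectation effect or regression to the mean. The contrast between the last two rows has the instruction on both sides, and a common effect cancels.

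**Pre/post test with no drug effect**

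Inputs from the document: 60 participants and 1:1 allocation, so 60/2 = 30 per arm; alpha 0.05. Assumed: a two-sided test (sidedness is not stated), and an instruction-only shift d in SD units of the within-person change. The document does not supply d, and it may be zero.

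For a paired t-test the noncentrality is d × √n, with √30 = 5.477. The critical value is t(0.975; 29) = 2.045. The chance of p < 0.05 is the noncentral t probability beyond ±2.045.

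| d | Noncentrality | Significant |
|---|---|---|
| 0 | 0 | 5% |
| 0.1 | 0.548 | 8.3% |
| 0.2 | 1.095 | 18.5% |
| 0.4 | 2.191 | 56.3% |

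A simulated Wilcoxon signed-rank test at the same four shifts gives 5, 8, 18 and 54%, so a non-parametric test does not avoid the problem. Pooling both arms (n = 60) raises the paired t figures to 33% at 0.2 SD and 86% at 0.4 SD.

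**Between-dose test with no drug effect**

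Simulated ANCOVA, 30 per arm, assumed baseline-to-treatment correlation 0.5:

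- Equal instruction effects in both arms, 0 to 0.6 SD: 4.7 to 5.0% significant, so the nominal rate holds.
- Instruction effects differing between arms by 0.1, 0.2 or 0.4 SD: 7, 15 or 42%.

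**Precision of the between-dose estimate**

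The unadjusted 95% CI half-width is t(0.975; 58) × √(2/30) = 2.002 × 0.258 = 0.52 SD. Baseline adjustment multiplies this by about √(1 − r²). With the assumed r = 0.5 that is 0.52 × 0.866 = 0.45 SD.

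**The case against.** The strongest reply has three parts.

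1. **An uncontrolled pilot cannot attribute any pre/post change to the drug, so this adds little.** It is true that the limit exists already, that the primary efficacy measure is the mGCSI-DD, and that the overall goal in section II is dose selection. What is particular here is that the protocol itself asks for the change it later scores.
2. **The instruction is sensible.** Reduction is limited to what is safe and tolerated, so a sustained fall may partly reflect better symptom control, and without a prompt habitual use could hide a benefit. That justifies giving the instruction. It does not supply the missing comparison: patients may have had room to cut as-needed use anyway, or may accept more symptoms when asked to.
3. **The test may be between doses.** Section XII can be read that way, and if so the main harm does not arise. The wording leaves it open, and section IV makes a within-group test plausible.

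A reader might also infer that breakthrough use is not recorded under treatment, because V.c does not list the form among the items handed out. The document does not support this. Bowel habits are to be reported through the study period on the same form as at baseline, V.b names one combined form for both, and section XI lists "mGCSI-DD score forms, medication usage and bowel habits forms" among the data. A reader might likewise suspect different instructions by arm, but V.c gives a single instruction to everyone.

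**Conclusion.** The point stands for the pre/post change in breakthrough use: a fall could come partly or wholly from the instruction, and nothing in the plan lets it be attributed to the drug. This rests on the stated sequence and the absence of an untreated arm, not on the percentages.

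The size is unknown. The 8, 19 and 56% figures assume no drug effect, 30 completers in an arm, a two-sided paired t-test and shifts of 0.1, 0.2 and 0.4 SD. The true shift could be nil.

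Three stronger readings go too far. It does not follow that an observed fall would be due to the instruction, since a drug effect could contribute. It does not follow that the dose comparison is biased; that would need the arms to respond differently to the instruction, which the document gives no ground to assume. Nor is it established that the plan will run a within-group test. This is a secondary endpoint with a cheap remedy, and it is worth correcting.

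**What to change.** 1. In section XII, define the analysis of breakthrough use as the high- minus low-dose difference over the 28 treatment days, adjusted for baseline-week use (ANCOVA, or a rank-based version if the data are strongly skewed), with a 95% CI. State one unit, such as days with any use per week, so that 7 baseline days and 28 treatment days are on the same scale.
2. State that pre/post change in breakthrough use is descriptive and is not evidence of efficacy.

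Both are wording changes and need no extra participants or visits. The costs are real:

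- A pre/post fall can no longer be claimed as benefit.
- The between-dose contrast suits the dose-selection goal but does not answer drug versus no treatment, and it would show nothing if both doses worked equally well.
- Precision is limited: besides the CI half-width of about 0.52 SD unadjusted, 80% power is reached only at about 0.72 to 0.74 SD.
- The contrast is free of instruction bias only if both arms respond alike. Participants are not told their dose, but the twice-daily and nightly schedules are visibly different.
- Any effect of reduced background medication on the mGCSI-DD remains. Less prokinetic or anti-emetic use could mask a benefit there, and these changes do not address it.
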